1.5 Sample Size Justification

Our collaborator, [name] employed n = 27 in the HFS-treated group and n=16 in non-treated group and observed a significant effect of HFS on SCFA production in type 2 diabetes mellitus (T2DM) study (1). Since the therapeutic effect of HFS may be different between MS and T2DM, we sought the assistance of [name] who is a Biostatistician at Rutgers University. We selected the published MS studies that showed the effect of high vegetable diet on development of Tregs (n=10 in each group in this study) (12), and calculated a reasonable sample size using mean and standard deviation of the data, assuming a mean difference of 5% type I error and 80% power. Our sample size calculation indicated that n=20 in each group is sufficient to observe the statistical difference in the development of regulatory cells. Although there is no published data on the effect of diet on intestinal permeability in MS, a study of intestinal permeability in MS (n=14) vs healthy donor (HD) (n=16) showed statistically significant increase in intestinal permeability in MS patients compared to HD (8). Our sample size calculation also indicated that n=20 in each group is sufficient to observe a statistical difference. Based on our previous HFS-data and sample size calculation, we propose to enrol 25 patients in each group in Aim-1. Regarding the sample size in Aim-3, there is no published intestinal inflammation biomarker data in MS. Therefore, we used the data from an IBD study (20) where n=20 was sufficient to detect

differences in Lcn-2, lactoferrin, and zonulin between IBD vs HD. From our sample size calculation we propose to enroll 25 patients in each group in Aim-3.

Summary:

Stool, and blood samples isolated from 50 MS patients and 50 healthy controls will be used for gut permeability, bacteria DNA sequencing, immunology experiments, and MS animal experiments.

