1.3 Research Design and Methods

RR-MS patients will be recruited from the Robert Wood Johnson Center for MS under the direction of [name]. The patients will be asked to participate in the study during their regular clinical visit to the MS Center.

Inclusion criteria includes patients aged 21-65 Relapsing Remitting Multiple Sclerosis (RRMS) who met the 2017 McDonald criteria.

The first group (**Group A**) of MS patients (**n=25**) will receive a dietary fiber supplementation. They will consume 60 g/day of HFS for 12 weeks (High-fiber supplement group, Group-A). The supplement consists of a mixture of soluble fibers (from inulin and fibersol-2) and insoluble fibers (from oat bran, corn bran, wheat bran and sorghum bran) and it will be consumed as a drink.

The second group of MS patients (**Group B**) (**n=25**) will not consume any high fiber supplement.

The first group (**Group C**) of healthy volunteers (**n=25**) will receive a dietary fiber supplementation. They will consume 60 g/day of HFS for 12 weeks. Healthy volunteers will not have MS.

The second group (**Group D**) of healthy volunteers (**n=25**) will not consume any high fiber supplement.

For Groups A, B, C & D stool, and serum samples will be collected at 3 time points (baseline; Week 8; & Week 12).

Group E (n=25) will consist of 25 subjects with MS who experience an MS flare up.

These 25 subjects can be those participants with MS who are already part of the above study (Group A or B) and consent to 2 extra blood and 2 extra fecal samples collected at the time of the acute flare up and upon resolution of symptoms.

Screening visits will typically take place during routine MS follow up visit at the Robert Wood Johnson Center for MS. During this time, eligibility will be reviewed, and consent will be obtained once the patient has had time to review the study, have questions answered, and agree to participate. During this screening visit, details regarding the patients MS history, food allergies/intolerances, medical history, and medications will be recorded. Eligible participants will be asked to provide blood and stool samples for baseline assessment.

A. Research Procedures

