Sept. 2021-Aug. 2023 Fecal transplantation in germ free mice and analysis for EAE

D. Endpoints

The primary endpoint will be detection of effect of HFS on intestinal microbial composition, intestinal permeability, production of SCFA, intestinal permeability, and immune cells in 25 MS patients between before and after intake of high-fiber supplement.

The secondary endpoint will be detection of biomarkers for intestinal inflammation-associated disease exacerbation in 25 MS patients.

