1.6 Study Variables

A. Independent Variables, Interventions, or Predictor Variables

Experiment 1: Four groups (HDs and MS patients with and without HFS treatment).

Experiment 2: Four groups (Fecal samples from HDs and MS patients with & without HFS treatment).

Experiment 3: Two groups (MS patients with MS relapse and healthy volunteers).

B. Dependent Variables or Outcome Measures

Experiment-1: Percentage of pathogenic and non-pathogenic bacteria, intestinal permeability, and percentage of pathogenic and regulatory immune cells.

Experiment-2: Incidence and severity of EAE development.

Experiment-3: Intestinal inflammation and intestinal permeability.

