4.3 Number of Subjects

A. Total Number of Subjects

50 MS patients and 50 healthy donors will be enrolled in this study. Please refer to section “1.5 Sample Size Justification” for calculation regarding sample size.

B. Total Number of Subjects If Multicenter Study – N/A

C. Feasibility

RWJ MS Center evaluates enough newly diagnosed MS patients every year to be able to recruit 50 MS patients for the study over 1 years. 50 healthy volunteers will be recruited from Rutgers students/staff and New Jersey local resident..

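### Baseline is sampled in Groups A to D, but no HFS-versus-no-HFS model is written and baseline enters no analysis as a covariate; its only stated inferential use is a before/after comparison in 25 MS patients

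*Combined protocol and SAP*

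**What the plan says.** Section 1.3 states that for Groups A to D "stool, and serum samples will be collected at 3 time points (baseline; Week 8; & Week 12". Its research procedures add that every MS patient and every healthy donor gives blood and stool at the baseline visit. Section 4.3 gives the total: "50 MS patients and 50 healthy donors will be enrolled in this study".

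Three places touch on how the outcomes will be used:

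- Section 1.3 D makes the primary endpoint the effect of HFS on microbial composition, permeability, SCFA and "immune cells in 25 MS patients between before and after intake of high-fiber supplement". This is a comparison within one group.
- Section 1.6 names four groups for Experiment 1 (MS and healthy, with and without HFS) and lists the outcomes as "Percentage of pathogenic and non-pathogenic bacteria, intestinal permeability, and percentage of pathogenic and regulatory immune cells".
- Section 1.5 sizes the study by group. From a published diet study the team "calculated a reasonable sample size using mean and standard deviation of the data", "assuming a mean difference of 5% type I error and 80% power". It concludes that "n=20 in each group is sufficient to observe the statistical difference in the development of regulatory cells" and then states "we propose to enrol 25 patients in each group in Aim-1".

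Section 6.1 Data Analysis carries no text. The only methods named for the human data are Random Forest and Partial Least Squares, in section 1.3 B, for microbiome biomarkers and prediction. The ANOVAs in the figure legends of section 1.4 belong to the previous diabetes work. No covariate is named anywhere.

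**The concern.** Groups B and D exist to show what happens over 12 weeks without the supplement. A before/after comparison in supplemented MS patients does not use them. It cannot separate the effect of HFS from drift, regression to the mean, season or assay batch. The natural estimates are A v B within MS and C v D within healthy donors, and neither is written down.

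Once such a contrast exists, someone must decide what to do with baseline, and the choice matters at 25 per group. Comparing follow-up levels ignores it. Comparing raw changes subtracts all of it, which adds noise when the baseline-to-follow-up correlation is below 0.5. Including baseline as a covariate uses it in proportion to its correlation with follow-up. With 6.1 blank, this choice could be made after the data are seen, separately for each of many outcomes.

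**Working it through.** **Inputs from section 1.5.** Type I error 5% (taken as two-sided; the plan does not say), power 80%, calculated n = 20 per group, planned n = 25 per group.

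**Inputs not given.** Mean difference, SD, and the baseline-to-follow-up correlation rho. The effect is therefore back-solved, and rho is an assumption shown from 0.3 to 0.8. No dropout or multiplicity allowance is applied.

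**The plan's own figure.** n = 20 cannot be reproduced, because the mean difference and SD are not printed. What can be found is the standardised effect d at which a two-sample t test (two-sided 0.05, 38 df) has 80% power with 20 per group: d = 0.909. The normal approximation gives (1.960 + 0.842) × √(2/20) = 0.886.

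**Formulas for two groups of 25.** With the follow-up SD set to 1 and equal baseline variance, the outcome variance is:

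- follow-up levels: 1
- raw change: 2(1 − rho)
- adjusted for own baseline: 1 − rho²

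Power comes from the noncentral t distribution with noncentrality (d / SD) × √(25/2), using 48 df for levels and change and 47 df for the adjusted model.

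**Results at d = 0.909, n = 25 per group**

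| rho | variance of change | variance adjusted | power, levels | power, change | power, adjusted | gain over levels | gain over change |
|---|---|---|---|---|---|---|---|
| 0.3 | 1.40 | 0.91 | 0.883 | 0.759 | 0.910 | 3 points | 15 points |
| 0.5 | 1.00 | 0.75 | 0.883 | 0.883 | 0.953 | 7 points | 7 points |
| 0.7 | 0.60 | 0.51 | 0.883 | 0.982 | 0.993 | 11 points | 1 point |
| 0.8 | 0.40 | 0.36 | 0.883 | 0.999 | 0.999 | 12 points | about 0 |

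Neither simple choice is safe when rho is unknown: change does badly at low rho and levels do badly at high rho.

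**If the unseen source SD is an SD of change.** Section 1.5 does not say which it is. The adjusted variance is then (1 − rho²) / (2(1 − rho)) = (1 + rho)/2 of the change variance. The gain over change runs from 9.3 points at rho 0.3 through 7.2 at 0.5 to 3.1 at 0.8 (normal approximation).

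**Sensitivity to baseline imbalance.** The factor 1 − rho² assumes similar baselines. A gap of δ baseline SDs between groups multiplies the adjusted variance by about 1 + δ²/4.

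- At rho 0.3 the gain over levels vanishes when 0.91 × (1 + δ²/4) = 1, so δ = √(4 × (1/0.91 − 1)) = 0.63.
- At rho 0.7 the gain over change vanishes when 0.51 × (1 + δ²/4) = 0.60, so δ = √(4 × (0.60/0.51 − 1)) = 0.84.

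**The case against.** The strongest reply is that the plan has not chosen an inefficient test; it has chosen none. That stands. A reader might infer from the per-group sizing in 1.5 and the outcome list in 1.6 B that unadjusted levels will be compared, at a fixed cost of 7 to 10 points of power. The documents do not support this. Section 1.6 B lists variables and is not an analysis. Section 1.5 does not say whether its mean and SD are of levels or changes. A figure of 7 to 10 points needs an assumed rho of about 0.5 to 0.6 and a comparison with levels. Against raw change, the closer match to a before/after use of baseline, the gain is about 1 point at rho 0.7.

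A reader might also infer that a baseline covariate helps whatever the contrast. It does not. For the stated one-group before/after endpoint, a two-group adjusted gain is undefined. For MS versus healthy, the baseline difference is itself of interest and should not be adjusted away.

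Two further replies also stand. No random allocation is described, so the precision argument rests on comparable baselines, and in non-randomised groups adjusted and change-score estimates can answer different questions. And on the back-solved effect, unadjusted power at n = 25 is already 88%.

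None of this removes the gap. The enrolment of Groups B and D and the four-group definition in 1.6 show that a comparison with and without HFS is intended. The 88% depends on an effect traced to a published study with 10 per group, before dropout or multiplicity.

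**Conclusion.** The point holds as a gap in the analysis plan. Baseline is available in Groups A to D, its only stated inferential use is before/after in 25 MS patients, and neither an HFS-versus-no-HFS model nor a baseline covariate is specified. Own-baseline adjustment of A v B and C v D makes better use of samples already planned.

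The size is illustrative: about 3 to 12 points of power over levels, and 15 down to about 0 over raw change, for rho 0.3 to 0.8. It rests on d = 0.909 back-solved from the plan's n = 20, a two-sided 5% test, an assumed rho, full follow-up and similar baselines. Imbalance would shrink the gain. Unless groups are randomised, the adjusted estimate should be read as an observational comparison. This is a change the plan should make, not a defect that invalidates the study.

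**What to change.** Write section 6.1. Define the HFS effect as A v B within MS and C v D within healthy donors. For each outcome, fit a linear model of the follow-up value on group plus the participant's own baseline value of that outcome. Name the visit (Week 8 or Week 12), or put both in a repeated-measures model. Use a log transform for skewed outcomes and a centred log-ratio (CLR) transform for compositional ones. Do not baseline-adjust MS-versus-healthy contrasts. State how participants are allocated to HFS or no HFS and, if not at random, that the estimate is observational. In 1.5, print the assumed mean difference, SD and rho, and say whether the SD is of levels or of change.

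Keep n = 25 per group. The cost is wording and one degree of freedom per model, with no new samples, visits or participants.

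### The primary endpoint in 1.3 D is a before/after change in 25 MS patients and leaves out the untreated MS group that is sampled at the same times

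*Combined protocol and SAP*

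**What the plan says.** Section 1.3 D states: "The primary endpoint will be detection of effect of HFS on intestinal microbial composition, intestinal permeability, production of SCFA". It then lists permeability a second time, adds immune cells, and sets the comparison "in 25 MS patients between before and after intake of high-fiber supplement". Group A is the only group of 25 MS patients that takes the supplement, so the sentence describes a within-group change in Group A.

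The rest of the plan describes a controlled design. Section 1.3 sets up untreated MS Group B (n=25) and says "For Groups A, B, C & D stool, and serum samples will be collected at 3 time points": baseline, week 8 and week 12. Section 1.6 names four groups, MS and healthy with and without supplement, as the predictor for Experiment 1. Section 1.5 sizes the study by group: "we propose to enrol 25 patients in each group in Aim-1".

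On permeability, section 1.5 opens with "Although there is no published data on the effect of diet on intestinal permeability in MS", continues "a study of intestinal permeability in MS (n=14) vs healthy donor (HD) (n=16) showed statistically significant increase", and concludes "Our sample size calculation also indicated that n=20 in each group is sufficient to observe a statistical difference". No difference, SD, test or sidedness is printed. The only error rate and power in the section belong to the preceding regulatory T-cell calculation: "assuming a mean difference of 5% type I error and 80% power".

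**The concern.** A change from baseline in treated patients mixes the effect of the supplement with anything else that moves over 12 weeks: season, background diet, disease course, assay batch, or regression to the mean. Group B is there to remove the part of this that both groups share, and its samples are already paid for. An endpoint sentence that omits it allows the main claim to rest on an uncontrolled comparison. The sponsor's own preliminary data (1.4 A) give a reason for care: in the diabetes study, 3 of the 15 SCFA producers were promoted in controls too. Those controls followed a recommended diet, so this is not a pure time trend, but it shows that change from baseline does not by itself isolate the supplement.

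Two further gaps make the primary result harder to read. Without a stated supplement effect on permeability, nobody can say what a null permeability result would rule out. Without a ranked variable or time, the reader cannot tell which result decides the study. Section 1.2 says success would justify launching a clinical trial, so a false positive would have consequences.

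**Working it through.** **Which comparison is primary**

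| Section | Comparison implied |
|---|---|
| 1.3 D | before v after, 25 MS patients |
| 1.5 | sizes each group |
| 1.6 A, Experiment 1 | four groups as predictor |
| 1.3, sampling | A, B, C and D at the same three times |

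The first row does not agree with the other three.

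**Effect of a time trend on the before/after test.** Inputs: n=25 (1.3 D); two-sided 5% (sidedness assumed); drift δ and within-patient correlation ρ assumed, since the documents give neither. Paired t-test, 24 df, standardised change dz = δ/√(2(1−ρ)), noncentrality dz×√25. True supplement effect: zero.

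| δ | ρ | dz | Chance of p<0.05 |
|---|---|---|---|
| 0.2 SD | 0.5 | 0.20 | 16% |
| 0.2 SD | 0.7 | 0.26 | 24% |
| 0.3 SD | 0.5 | 0.30 | 30% |
| 0.3 SD | 0.7 | 0.39 | 46% |

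In A versus B, a drift common to both groups cancels and the rate returns to 5%.

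**The plan's n=20 for permeability.** It can be neither reproduced nor refuted, because no difference or SD is printed. Worked backwards, assuming 80% power and two-sided 5%, the normal approximation gives d = (1.960+0.842)×√(2/20) = 0.89 SD; the t-test gives 0.91 SD. Significance at 14 v 16 does not by itself lead to 20: the smallest significant difference there is t(0.975, 28)×√(1/14+1/16) = 0.75 SD, which would need about 29 per group. With 25 per group unpaired, a supplement effect of the full 0.91 SD has 88% power and half of it has 35%. Nothing in the documents ties the supplement effect to that scale.

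**Power of the two contrasts for the same effect.** Take half of 0.909, that is 0.45 SD, and n=25 per group. The before/after test is as above, assuming no drift. A versus B adjusted for baseline has residual SD √(1−ρ²), 47 df, and noncentrality 0.45/√(1−ρ²)×√(25/2).

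| ρ | Before/after | A v B adjusted |
|---|---|---|
| 0.5 | 59% | 44% |
| 0.7 | 80% | 60% |

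**Difference detectable with 80% power, 25 analysed per group, A versus B, two-sided**

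| ρ | Single primary, α=0.05 | Strictest Holm step over four, α=0.05/4=0.0125 |
|---|---|---|
| 0 | 0.81 SD | 0.98 SD |
| 0.5 | 0.70 SD | 0.85 SD |
| 0.7 | 0.58 SD | 0.70 SD |

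**Multiplicity.** Section 1.3 D lists five items. With permeability counted once there are four domains: microbial composition, permeability, SCFA and immune cells. If any single 5% result counted as success, four independent tests give 1−0.95⁴ = 18.5%; at a correlation of 0.5 between domains, simulation gives about 16%. Testing at both weeks, or several markers per domain, would raise this.

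**The case against.** The strongest reply is that a controlled comparison is already foreseen. Section 1.3 B plans similar samples from the untreated group, Experiment 3 analyses treated and untreated MS patients at all three times, and 1.6 makes the four groups the predictor. That is correct. A reader might infer from 1.3 D that Group B will be ignored, and the documents do not support that. The defect is one endpoint sentence that disagrees with its surroundings. Because it is the sentence that defines the primary result, it still needs correcting.

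The drift of 0.2 to 0.3 SD has no source in the documents. This stands: the 16 to 46% shows sensitivity and does not estimate this trial's error rate.

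On permeability, a reader might infer that 20 or 25 per group is too few, or that no supplement effect on permeability is known. Neither follows. The inputs are unprinted, and the link to the MS-versus-healthy study is inferred from its position in the paragraph. MS versus healthy is also a legitimate comparison in this design. Section 1.5 says only that nothing is published on diet and permeability in MS; it also appeals to earlier data on the supplement, whose content cannot be seen. What can be said is that no such effect is given.

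On multiplicity, the study is largely mechanistic and states no rule for success, so the 16 to 19% depends on an assumed rule. A reader might also infer that the plan has no error control. The heading 6.1 Data Analysis has no text as supplied, which may be an extraction loss, so that cannot be asserted. The lack of ranking within 1.3 D does not depend on 6.1.

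**Conclusion.** The main point holds with high confidence. Section 1.3 D sets an uncontrolled before/after contrast as primary, in conflict with 1.5 and 1.6, while the concurrent untreated MS group is sampled on the same schedule. The inflation of 16 to 46% rests on assumed drift and correlation.

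The two supporting points carry less weight. Power for a supplement effect on permeability is not demonstrated, which is weaker than saying the sample is inadequate. The four domains and two times are unranked, at a cost of about 16 to 19% for four tests, and only under an any-one-counts rule that the plan does not state. This should be corrected before analysis; it does not call for a larger trial.

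**What to change.** - **1.3 D, contrast.** Make Group A versus Group B at week 12, adjusted for baseline, the primary comparison, with before/after in Group A as supportive. State how patients come to be in A or B. The supplied text does not say that they are randomised; if they are not, say that confounding remains possible after baseline adjustment.
- **1.3 D, variables.** Either name one primary variable at week 12 with the others secondary or exploratory, or keep one prespecified variable per domain under Holm. Delete the second mention of permeability. The choice is the sponsor's.
- **1.5, permeability.** Replace the sufficiency sentence with a statement that no supplement effect on permeability is given. Add the difference detectable with 25 analysed per group (80% power, two-sided 5%, before dropout) for the analysis actually chosen: 0.81, 0.70 or 0.58 SD at baseline correlations of 0, 0.5 or 0.7 for a single primary; 0.98, 0.85 or 0.70 SD at the strictest Holm step over four domains. The figure must match the choice made in 1.3 D, or a new inconsistency is created.

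Enrolment and sampling do not change. The cost is power on paper, as tabulated above: the controlled contrast has 15 points less than before/after at correlation 0.5 (59−44) and 20 points less at 0.7 (80−60), and the before/after advantage holds only if there is no drift. A single primary moves three domains out of the primary set; Holm keeps them but raises the detectable difference at its strictest step.

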1.6 Study Variables

A. Independent Variables, Interventions, or Predictor Variables

Experiment 1: Four groups (HDs and MS patients with and without HFS treatment).

Experiment 2: Four groups (Fecal samples from HDs and MS patients with & without HFS treatment).

Experiment 3: Two groups (MS patients with MS relapse and healthy volunteers).

B. Dependent Variables or Outcome Measures

Experiment-1: Percentage of pathogenic and non-pathogenic bacteria, intestinal permeability, and percentage of pathogenic and regulatory immune cells.

Experiment-2: Incidence and severity of EAE development.

Experiment-3: Intestinal inflammation and intestinal permeability.

